6.3 Patient randomization and assignment to treatment arm

The study will accrue up to 60 patients with a 1:1:1:1 ratio to include 4 intervention arms. Those include conventional therapy, conventional therapy + MB 0.025%, conventional therapy + MB 0.05%, and conventional therapy + MB 0.1%; each group will include 15 patients. We will conduct stratified randomization by baseline pain (baseline NRS 0-5 vs. 6-10) and oral functioning score (0-3 vs. 4-6). The primary endpoint is the reduction in pain score from baseline to 7 days. Patient randomization will be done through the Clinical Trial Conduct website. Study staff will be uninvolved in the randomization process.

Once a patient is enrolled in the study, the Investigational Pharmacy at MDACC retrieves the randomized treatment arm information from the Clinical Trial Conduct website. Once a patient is randomized to a treatment arm, Investigational Pharmacy will relay the information to the dispensing pharmacy at MDACC.

Study staff will contact patients either in person if as an inpatient or by phone at every follow-up the encounter to check for adverse events during routine patient encounters or via telephone calls.

Patients who were randomized to conventional arm will have an option to cross over to one of 3 MB arms, which they will be randomly allocated to, after completing 2 day pain measurements.

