6.5 Data collection

Patients enrolled in the study will be asked to complete a baseline assessment questionnaire in person, including the Modified Harris mucositis-related pain assessment tool. The patient will have subsequent follow-up interviews at 1, 2, 7 days with repeat assessment of the Modified Harris mucositis-related pain assessment tool. Furthermore, on Baseline, Day 0, Day 1, Day 2, Day 7 and Day 30, adverse event will be assessed, and this maybe by telephone or face-to-face in the clinic. The patient's medication use will also be assessed at follow-up, including morphine equivalent daily dose (MEDD) and other reported analgesics used for the treatment of their mucositis-related pain. Lastly, the research team will investigate if any patient reported any side effects from the treatment.

All completed data will be stored electronically in the MD Anderson REDCap system, in a locked file, on password-protected computers. Only research team members will access the files. Subject registration will be entered into CORe database.

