6.51 Modified Harris mucositis-related pain assessment tool (MHMPAT)

Among the numerous scales utilized for assessment of mucositis, most do not incorporate pain. The original Harris mucositis-related pain assessment tool was developed to fill the void of inadequate assessment of mucositis associated pain in existing assessment tools (18). The scale includes the NRS, which is one of the most widely utilized pain assessment measures in research and clinical care (17). Its use is related to its ease of administration. It uses an 11-point scale for measuring pain intensity (0 representing no pain, to 10 representing the worst possible pain). It is also beneficial for the current study, as it can accurately assess pain during telephone interview (17).

For this study we developed the Modified Harris mucositis-related pain assessment tool which has not yet been validated but incorporates aspects of many validated tools. It has been adapted with permission from the creator, [name], MSN, and OCN.

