7.2 Primary Outcome Analysis

Descriptive statistics (means (SDs) or counts (percent)) will be used to summarize demographics, disease, and treatment variables according to the intervention arm. Potential differences between the arms based on demographic, disease, and treatment variables will be explored using Chi-square test or Fisher's exact test for categorical variables and ANOVA or Kruskal-Wallis test for continuous variables, depending upon the nature of the variables being investigated.

Our primary endpoint is the reduction in pain scores assessed within the NRS component of the Modified Harris mucositis-related pain assessment tool from baseline to 7 days which is considered the end of the study. The mean change in scores will be compared among 4 arms, utilizing ANOVA. If there are significant differences between intervention arms in some covariates, a linear regression model will be utilized to compare arms by adjusting for those significant covariates. The mean pain scores over time will be compared among study arms, utilizing linear mixed effects models. Covariates that showed significant differences among study arms will be adjusted in the linear mixed effects models. Two separate analyses, intention to treat and per protocol, will be conducted for primary analysis. Tukey's pairwise comparison will be conducted if a significant difference is observed among 4 arms. Intention to treat analysis population will include all patients who were randomized to one of treatment groups regardless of completion of the treatment. Per protocol analysis will include those patients who completed the treatment originally allocated. Patients who did not have 7day NRS will be replaced.

Patients who were initially enrolled in conventional arm and crossed over to one of MB arms will be included in assigned MB arm.

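### Section 7.2 replaces patients who lack a Day 7 NRS and gives no method for the missing score, so the ANOVA labelled ITT compares only patients observed at Day 7, substitutes included.

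*Combined protocol and SAP*

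**What the plan says.** Section 7.2 (Primary Outcome Analysis) names two primary analyses, ITT and per protocol. For ITT it says: "Intention to treat analysis population will include all patients who were randomized to one of treatment groups regardless of completion of the treatment". The test of the primary endpoint, the reduction in NRS from baseline to Day 7, is stated as: "The mean change in scores will be compared among 4 arms, utilizing ANOVA". For a missing Day 7 score, it says only: "Patients who did not have 7day NRS will be replaced".

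Neither document section gives an imputation rule or a sensitivity analysis for missing scores, or says whether a replaced patient stays in the ITT set. Replacement is mentioned nowhere else.

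Section 7.2 also lists a longitudinal analysis: "The mean pain scores over time will be compared among study arms, utilizing linear mixed effects models". It is not named as the ITT estimate at Day 7 or as the method for missing scores.

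Section 6.5 schedules "subsequent follow-up interviews at 1, 2, 7 days with repeat assessment", and section 6.3 has staff contact patients "either in person if as an inpatient or by phone at every follow-up". Section 6.3 caps accrual at 60 without saying whether that counts patients randomised or patients with a Day 7 score. Sections 5.1 and 7.1 base the 83% power on 15 patients per arm.

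**The concern.** The replacement rule and the ITT definition cannot both govern the same ANOVA. A change score needs a Day 7 value. With no rule to supply one, the test drops the patient, whatever the population is called. What is left is a comparison of patients observed at Day 7, topped up with substitutes who were also observed.

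If the reason for a missing score is related to pain outcome, and loss is heavier in some arms than in others, the arm means shift by different amounts. Substitutes come through the same filter, so refilling to 15 restores the sample size and leaves the shift in place. Unequal loss is conceivable here because section 5.0 blinds only the concentration: under section 4.0 the control arm has no MB rinse for the first 2 days, so patients know whether they are using one.

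**Working it through.** **1. The plan's own power.** Inputs from section 7.1: means 0, 2, 2.5, 3; within-group SD 2.5; 15 per arm; alpha 0.05.

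- Grand mean 1.875; squared deviations sum to 3.516 + 0.016 + 0.391 + 1.266 = 5.1875.
- SD of the means = √(5.1875/4) = 1.139 (stated 1.14).
- Noncentrality = 15 × 5.1875 / 2.5² = 12.45, with 3 and 56 degrees of freedom.
- Power = 82.7% (stated 83%).

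The figure reproduces. It requires 15 Day 7 scores in every arm.

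**2. What the cap of 60 implies.** No dropout rate is given, so 10%, 20% and 30% are assumptions.

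| Missing Day 7, all arms | ANOVA power if 60 are randomised | Randomised per arm for 15 scores, 15/(1−d) rounded up | Total |
|---|---|---|---|
| 10% | 77.7% | 17 | 68 |
| 20% | 71.7% | 19 | 76 |
| 30% | 64.6% | 22 | 88 |

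If 60 counts randomised patients, replacement after the 60th breaks the cap. If it counts Day 7 scores, more than 60 must be randomised.

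**3. Shift from selective loss.** Suppose the fraction d lost in an arm are those lowest on a trait that has correlation ρ with the Day 7 reduction (SD 2.5). With z the d-quantile of the standard normal and φ its density:

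- shift of the observed mean = ρ × 2.5 × φ(z)/(1−d)
- retained minus lost = ρ × 2.5 × φ(z)/[d(1−d)]

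| d | Shift, ρ = 0.5 | Shift, ρ = 0.3 | Retained minus lost, ρ = 0.5 | ρ = 0.3 |
|---|---|---|---|---|
| 10% | 0.244 | 0.146 | 2.44 | 1.46 |
| 20% | 0.437 | 0.262 | 2.19 | 1.31 |
| 30% | 0.621 | 0.373 | 2.07 | 1.24 |

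These are strong assumptions: at ρ = 0.5 the lost patients do worse by about the size of the smaller planned treatment effects. The bias in a contrast is the difference between two arms' shifts. With control 10% and MB 20% it is 0.437 − 0.244 = 0.19 points (0.12 at ρ = 0.3). With control 10% and MB 30% it is 0.38 (0.23). Planned control–MB differences are 2 to 3 points.

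**4. Type I error of the ANOVA.** 200,000 simulated trials per case, no true difference, arms refilled to 15 under the same selection:

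| Loss: control / MB arms | Gap (points) | ρ = 0.5 | ρ = 0.3 |
|---|---|---|---|
| 20% / 20% | 0 | 5.0% | 5.0% |
| 10% / 20% | 10 | 5.4% | 5.3% |
| 20% / 30% | 10 | 5.3% | 5.1% |
| 10% / one MB arm 20%, others 10% | 10 | 5.4% | 5.2% |
| 0% / 10% | 10 | 5.6% | 5.2% |
| 10% / 30% | 20 | 6.7% | 5.5% |
| 0% / 20% | 20 | 7.2% | 5.7% |
| 0% / 30% | 30 | 9.7% | 6.5% |

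Equal, equally selective loss cancels. A separate simulation that sets the difference between lost and retained patients directly gave about 7% at 2 points and 11% at 3 points, with 5% loss in control and 30% in each MB arm.

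**5. Does the mixed model help?** Loss of 0% in control and 20% in MB, Day 2 and Day 7 changes correlated 0.5 or 0.7, no replacement and no crossover, 20,000 runs:

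| Loss driven by a trait correlated 0.5 with | Bias, observed-score ANOVA | Bias, mixed model |
|---|---|---|
| Day 2 change | 0.21 or 0.30 | −0.01 or 0.00 |
| Day 7 change | 0.43 | 0.33 or 0.22 |

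In the first case the bias goes. In the second, the model removes (0.43 − 0.33)/0.43 = 23% or (0.43 − 0.22)/0.43 = 49% of it.

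**The case against.** The best defence is that replacement is only an accrual rule. Section 7.3 counts evaluable patients per arm for its safety reports, and the replacement sentence directly follows the per-protocol definition, so it may mean enrolling until 15 per arm have a Day 7 score. That reading is reasonable, and the documents do not support inferring that replaced patients are deleted from the ITT set. It does not rescue the ANOVA, which still cannot use a patient without a Day 7 score.

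Second, loss over seven days may be low. Every patient has a Day 7 interview, section 7.3 names the telephone for it, and section 6.51 says of the NRS that "it can accurately assess pain during telephone interview". Section 6.4 expects the supply to run out in 2 to 3 days of regular use, so Day 7 normally falls after rinsing has ended anyway. All this stands and limits the likely size. A reader might take the dropout comparison in section 7.3 as evidence that the sponsor expects unequal missing Day 7 scores. It is not: that section offers it as a measure of compliance with MB. The right to withdraw in section 5.4 is standard wording, and leaving care at the centre (section 9.0) matters only if it happens within the week.

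Third, the mixed model is already in the plan. True, but nothing links it to the ITT contrast at Day 7.

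**Conclusion.** The point holds as an internal conflict: the stated ITT population and the replacement rule do not fit the same change-score ANOVA, and no missing-data method closes the gap. It should be settled before analysis, because deciding afterwards who counts would be post hoc.

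The expected effect is modest. It rests on assumed loss rates and an assumed link between loss and outcome. The documents supply neither, and they support no particular gap of 20 to 30 points. A reader might infer that the primary result will be biased in favour of MB, or that its error rate is seriously inflated. The documents show neither: direction and size are unknown. Nor is this an error in the sample size calculation, which reproduces.

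A separate defect sits beside this one: "Patients who were initially enrolled in conventional arm and crossed over to one of MB arms will be included in assigned MB arm". While that sentence stands, no contrast is fully ITT, however missing scores are handled. It needs its own resolution, and its power cost is not counted here.

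**What to change.** 1. Restate replacement in section 7.2 as additional enrolment only, with the replaced patient kept in the ITT set. In section 6.3, say whether 60 counts randomised patients or patients with a Day 7 score, and note that 83% power needs 15 Day 7 scores per arm.
2. Estimate the ITT Day 7 contrast from the planned linear mixed model (Days 0, 1, 2 and 7, arm by visit), so that patients missing Day 7 contribute their earlier scores. Keep the observed-score ANOVA as a supporting analysis.
3. Collect the Day 7 NRS by telephone also from patients removed from the study, unless consent is withdrawn.
4. Add one sensitivity analysis for missing Day 7 scores, since the mixed model only partly corrects loss that depends on the Day 7 score itself. Counting a missing score as zero reduction is one option. Because zero is the assumed control mean, this lowers only the MB arms: at 10% missing, expected differences of 2 to 3 become 2 × 0.9 = 1.8 to 3 × 0.9 = 2.7. The plan should say so.

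The cost is slightly more analysis and a few more calls. Power does not suffer: with 10%, 20% or 30% missing at random from 60 randomised, simulated mixed-model power is about 78%, 74% and 67% (Day 2–Day 7 correlation 0.5) or 79%, 76% and 71% (correlation 0.7), against 77.7%, 71.7% and 64.6% for the ANOVA. If 60 is meant to count Day 7 scores, the extra enrolment in step 2 of the working applies.

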2.0 Study Objective

The primary objective is to evaluate the efficacy of MB in reducing the severity of mucositis-related pain, measured by Numeric Rating Scale (NRS), in cancer patients who underwent or are undergoing chemotherapy or radiation therapy. Patients will be randomized to one of 4 intervention arms, including conventional therapy and conventional therapy plus MB with one of 3 concentrations (0.025%, 0.05% or 0.1%) oral rinse to swish and spit.

2.1 Primary Outcomes:

Oral mucositis pain reduction (measured by using the Numeric Rating Scale (NRS); from 0, representing no pain, to 10, representing the worst possible pain) from baseline to 7 days post treatment. The pain scale is included in the Modified Harris mucositis-related pain assessment tool.

2.2 Secondary Outcomes:

1. Oral functioning (eat, swallow, talk: unable=2, difficulty=1, able=0. Oral functioning score is the total score of 3 categories, ranged 0-6). Scale is included in the Modified Harris mucositis-related pain assessment tool. Measurements are obtained at day 0, 1, 2, and 7.
2. Presence of absence of pain and pain score measured by NRS at day 0, 1, 2, and 7.
3. Number of MB doses needed to achieve pain relief at 0, 1, and 2 days post MB administration
4. Morphine equivalent daily dose (MEDD) used for oral mucositis pain at 2, and 7 days post MB administration.
5. Incidence of untoward side effects immediately after MB administration and at 1, 2, 7 days post MB administration.

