4.0 Study Design

This study is a prospective, randomized trial involving adult patients with intractable pain associated with oral mucositis. This study will have four intervention arms - MB 0.025 arm, MB 0.05 arm, MB 0.1 arm and a control arm. MB arm will receive one of 0.025%, 0.05% or 0.1% MB solution in addition to conventional therapy (0.025%, 0.05%, and 0.1% MB solution for MB 0.025, MB 0.05, and MB 0.1 arm, respectively), and the control arm will receive conventional therapy for 2 days, then will receive one of 3 solutions which will be randomly selected if they would like to receive MB solution.

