7.0 Data Analysis

Demographic information along with effectiveness data will be used to determine if there is a difference between the conventional care alone and the use of MB in addition to conventional care for the treatment of intractable pain associated with oral mucositis.

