7.1 Sample Size Justification and Randomization

In a one-way ANOVA study, sample sizes of 15, 15, 15, and 15 are obtained from the 4 groups whose means are to be compared. The total sample of 60 subjects achieves 83% power to detect differences among the means versus the alternative of equal means using an F test with a 0.05 significance level. The size of the variation in the means is represented by their standard deviation which is 1.14 (means of 0, 2, 2.5, and 3 for conventional therapy, conventional therapy + MB 0.025, conventional therapy + MB 0.05, and conventional therapy + MB 0.1, respectively). The common standard deviation within a group is assumed to be 2.5. We will conduct stratified randomization by baseline pain (baseline NRS 0-5 vs. 6-10) and oral functioning score (0-3 vs. 4-6).

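### Controls who choose MB after day 2 are counted in an MB arm at day 7, so the primary MB-versus-control comparison is as-treated although it is called intention to treat

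*Combined protocol and SAP*

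**What the plan says.** Section 6.3 gives controls an "option to cross over to one of 3 MB arms, which they will be randomly allocated to, after completing 2 day pain measurements". Section 4.0 confirms that this is voluntary: after two days on conventional therapy, the control patient "then will receive one of 3 solutions which will be randomly selected if they would like to receive MB solution". The primary endpoint is the change in NRS pain from baseline to day 7, five days after crossover opens.

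Section 7.2 compares the four arms by ANOVA, adds a mixed model for pain over time, and calls for both an intention-to-treat (ITT) and a per-protocol analysis. It defines the first set by inclusion only: "Intention to treat analysis population will include all patients who were randomized to one of treatment groups regardless of completion of the treatment". For the second: "Per protocol analysis will include those patients who completed the treatment originally allocated". It closes with a sentence tied to neither set: "Patients who were initially enrolled in conventional arm and crossed over to one of MB arms will be included in assigned MB arm".

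Section 7.0 gives the purpose of the analysis as to "determine if there is a difference between the conventional care alone and the use of MB in addition to conventional care". On size, Section 7.1 says: "The total sample of 60 subjects achieves 83% power to detect differences among the means".

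**The concern.** Patients decide whether to cross after seeing how the first two days went. If those who cross are moved into the MB arms, randomisation no longer determines who is compared with whom. If the least-improved controls cross, the remaining controls look better and MB looks worse; if the most-improved cross, MB is flattered. If all 15 cross, the four-arm ANOVA has no control arm. The contrast exposed is the one that Section 7.0 names as the purpose.

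The comparison among the three concentrations is much less affected, because crossovers are allocated to a concentration at random, although they start MB two days late.

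Section 7.2 also does not say whether a crossover's baseline is reset, or where their day 0 to 2 scores go in the mixed model.

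**Working it through.** **Inputs from the documents.** 15 patients per arm; mean reductions 0, 2, 2.5 and 3; SD 2.5; F test at 0.05 (Sections 5.1 and 7.1). Crossover opens after day 2 (Section 6.3); the endpoint is at day 7.

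**Assumptions, because the documents give no figures.** 3, 8 or 12 of 15 controls cross; the correlation r between day-2 and day-7 change is 0.5 or 0.7. Crossovers are split as evenly as possible over the MB arms and take that arm's effect. The day-0 baseline is kept unless stated.

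**Step 1: the stated power.** The mean of the four means is 1.875. The squared deviations are 3.516, 0.016, 0.391 and 1.266, which sum to 5.1875. The SD of the means is √(5.1875/4) = 1.139 (stated 1.14). The noncentrality is 15 × 5.1875 / 2.5² = 12.45, and with 3 and 56 degrees of freedom power is 0.827 (stated 83%). The plan's figure reproduces, but only with 15 controls who stay untreated with MB.

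**Step 2: bias under the rule if MB has no effect.** Let the 8 least-improved controls cross. The 7 who stay have an expected day-7 mean of m = r × 2.5 × 0.809, where 0.809 is the expected mean of the top 7 of 15 standard normal values. That is 1.01 at r = 0.5 and 1.42 at r = 0.7. All 15 controls average 0, so the crossers' sum is −7m, spread over 45 + 8 = 53 MB patients. MB minus control is therefore −m(1 + 7/53), which is −1.14 (r = 0.5) and −1.60 (r = 0.7).

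**Step 3: rejection rates if MB has no effect.** Simulation, 40,000 runs per scenario; each pair is r = 0.5, then r = 0.7.

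| Scenario, rule as written | Rejection | Bias (NRS points) |
|---|---|---|
| 3 least-improved cross | 6.9%, 9.2% | −0.51, −0.72 |
| 8 least-improved cross | 12.5%, 21.8% | −1.14, −1.61 |
| 12 least-improved cross | 12.6%, 21.2% | −1.73, −2.41 |
| 8 cross, choice only partly driven by day 2 | 8.5%, 12.4% | not tabulated |
| 8 most-improved cross | 12.4%, 21.7% | +1.15, +1.59 |
| 8 least-improved cross, their baseline reset to day 2 | 9.4%, 17.2% | −0.87, −1.33 |
| 8 least-improved cross, test among the three concentrations only | 4.6%, 4.7% | not applicable |

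Analysed as randomised, rejection is 4.8% to 5.2% throughout. With the 8 least-improved crossing, about 98% to 99.6% of the rejections show MB worse. At r = 0.3 the rate for 8 crossing is 8%. With the baseline reset and r = 0, the bias turns to +0.26.

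**Step 4: power if the planned effects are real.**

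| Controls crossing | Rule, crossing unrelated to outcome | As randomised, crossing unrelated to outcome | As randomised, least-improved cross |
|---|---|---|---|
| 0 | 83% | 83% | 83% |
| 3 | 77% | 62% | 66%, 67% |
| 8 | 60% | 27% | 33%, 35% |
| 12 | 37% | 14% | 17%, 17% |

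If the 8 least-improved cross, the written rule has 27% and 19% power and estimates an average effect of 1.36 and 0.90 points instead of 2.5. As-randomised analysis of the same data is diluted as well: the control mean becomes (8/15) × 2.5 = 1.33, so the estimate is 2.5 − 1.33 = 1.17.

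**Step 5: the day-2 contrast.** Crossover has not yet begun at this assessment. If the day-2 effect is 100%, 75% or 50% of the planned day-7 effect (assumed), the noncentrality is 12.45, 7.00 or 3.11 and power is 83%, 56% or 27%.

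**The case against.** The crossover sentence names no analysis set, so a settled as-treated ITT analysis is an inference. That is fair, but the sentence sits in the primary analysis section without qualification, and nothing exempts the ITT analysis.

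Section 4.0 could be read as making optional MB part of the control regimen, so that a crossover did complete the allocated treatment. Even so, such a patient would belong in the control arm, not in an MB arm.

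Section 5.1 counts seven days from study entry and Section 6.5 describes a single baseline assessment. Both point to the day-0 baseline, so that gap is small; the fix only makes it explicit.

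Day-2 pain is already a secondary outcome (Section 2.2: "Presence of absence of pain and pain score measured by NRS at day 0, 1, 2, and 7"). True, but under the crossover sentence its analysis need not follow the randomised arms.

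The strongest objections concern size and direction. In patients with intractable pain, those who improve least are the natural crossers, and that selection works against MB, so a false claim of efficacy is not the likelier error. The 13% to 22% also assumes strict ranking on day-2 improvement; milder assumptions give 7% to 12%. Both points stand. A biased estimate that can hide a real effect is still a failure of the primary analysis.

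Finally, the fix costs power, and if crossing is unrelated to outcome the written rule does better (60% against 27% at 8 of 15). That also stands, but the assumption cannot be tested. If the least-improved cross, the rule has less power than as-randomised analysis.

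**Conclusion.** The concern holds and must be fixed before outcomes are examined. As written, the day-7 MB-versus-control comparison depends on a patient choice made after randomisation. With 8 of 15 controls crossing according to day-2 improvement, type I error is 13% to 22% and bias is 1.1 to 1.6 NRS points, in a direction set by who crosses. These sizes rest on assumed crossover numbers, selection patterns and correlations. If crossing is unrelated to outcome, type I error stays at 5% and only power falls. The departure from randomisation does not depend on those assumptions. The stated 83% power is arithmetically right, but it holds under neither analysis once controls cross and benefit.

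**What to change.** Replace the last sentence of Section 7.2 with: *All patients are analysed in the arm to which they were originally randomised, in the ANOVA and in the mixed model. Data from crossovers after day 2 do not contribute to any MB-arm estimate; they are reported separately and descriptively as change from day 2 by concentration, with adverse events attributed to MB exposure.*

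Also:
- State that baseline is the day-0 value for everyone in the randomised comparison.
- State in Sections 5.1 and 7.1 that 83% power holds only without crossover.
- Report the day-2 NRS comparison by randomised arm as the undiluted MB-versus-control contrast.

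The cost is SAP wording, one descriptive table and one explicit day-2 contrast on data already collected. The fix restores type I error to about 5% but not power: if crossovers gain the full planned effect, day-7 power is about 62% to 67%, 27% to 35% or 14% to 17% with 3, 8 or 12 crossing. The underlying cause is that crossover opens before the primary endpoint. Whether to move that endpoint to day 2 is a separate design decision for the sponsor.
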